4.9.2. Additional Secondary Efficacy Analysis	20
4.11. Safety Analyses.....	23
4.11.1. Extent of Exposure and Treatment Compliance	25
4.11.2. Adverse Events	25
4.11.3. Narratives	27
4.11.4. Additional Safety Assessments	28
4.11.5. Clinical Laboratory Evaluations	33
4.11.6. Vital Signs, Physical Findings, and Other Observations Related to Safety	34
4.11.7. Device Product Complaints	34
4.12. Other Analyses.....	34
4.12.1. Subgroup Analyses	34
4.13. Interim Analyses	35

4.11. Safety Analyses.....	23
4.11.1. Extent of Exposure and Treatment Compliance	25
4.11.2. Adverse Events	25
4.11.3. Narratives	27
4.11.4. Additional Safety Assessments	28
4.11.5. Clinical Laboratory Evaluations	33
4.11.6. Vital Signs, Physical Findings, and Other Observations Related to Safety	34
4.11.7. Device Product Complaints	34
4.12. Other Analyses.....	34
4.12.1. Subgroup Analyses	34
4.13. Interim Analyses	35

5.	Sample Size Determination	36
6.	Supporting Documentation	37
6.1.	Appendix 1: Searching Criteria for Adverse Events of Special Interest (AESI).....	37
7.	References.....	38

Version history

This Statistical Analysis Plan (SAP) for study I8F-MC-GPIU (GPIU) is based on the protocol amendment (b) dated 05 December 2023.

Table 1.1. SAP Version History Summary

SAP Version	Approval Date	Change	Rationale
1	31 January 2024	Not Applicable	Original version
2		
Section 4.1:
 
 Revise the analysis software as: “All statistical analyses will be conducted with SAS Version 9.4 or higher and R Version 4.1.2 or higher unless otherwise stated.” Add baseline definition for lab and patient reported outcome: “Baseline is defined as the last non-missing measurement recorded on or before the randomization visit, prior to first dose of treatment, unless otherwise specified. For lab, baseline needs to be prior to or within one hour after the first dose time. For patient reported outcomes, data collected at Visit 3, regardless of the timing relative to first dose, will serve as baseline.” 
Section 4.8.3:
 
 Removed baseline*visit interaction in MMRM 	
 Added for clarification Changed to minimize missing baseline data relevant to dosing.

SAP Version	Approval Date	Change	Rationale
			interaction to avoid possible model convergence issue and keep consistent with all the SURPASS studies.
		Section 4.11.3: 
 Pregnancy and AESI added as notable events 	
 Add additional criteria for patient narrative
		Section 4.11.4.13: 
 Onset plots added: “The time courses of prevalence, and incidence and onset (newly-occurring episodes) of nausea, vomiting, diarrhea, and combined will be plotted by treatment and maximum severity.” The following description added: “The gastrointestinal TEAE will also be summarized by participants with de-escalation or not.” 	
 Added onset plots and de-escalation related analysis for GIAE
		Section 4.11.7 added for product complaint	
 Add description for product complaint analysis
		Section 4.12.1: 
 Removed treatment regimen estimand from subgroup analysis: 	
 Efficacy estimand is sufficient for subgroup

SAP Version	Approval Date	Change	Rationale
		
“Efficacy subgroup analyses will be guided by the treatment regimen estimand and efficacy estimand. ”
 
 Revised the wording: “Subgroup analyses of the change in HbA1c and the change in weight from baseline to Week 40 willmay be made to assess consistency of the intervention effect across the following subgroups” Duration of diabetes subgroup revised from “≤5 vs >5 to ≤10 years vs >10 years” to “≤5 vs >5 years” Subgroup analysis of treatment-emergent adverse event added 	
analysis to explore subgroup efficacy results.
 
 Flexible wording to reflect planned subgroup analysis Due to the limited number of participants in “>5 to ≤10 years” and “>10 years”, these two groups were combined Added subgroup analysis for TEAE

1. Introduction

Study GPIU (monotherapy) is a Phase 3, multicenter, randomized, double-blind, parallel, placebo-controlled, 40-week study that investigates the efficacy and safety of 3 doses of tirzepatide compared with placebo in Chinese participants with T2DM, inadequately controlled with diet and exercise alone, and have not been treated with any antihyperglycemic medication during the 90 days preceding the start of the study. This study aims to provide evidence of the tirzepatide as monotherapy for the treatment of Chinese patients with T2DM in early phase.

1.1. Objectives, Endpoints, and Estimands

Objectives	Endpoints
Primary	

 • To demonstrate that tirzepatide QW 5 mg, and/or 10 mg, and/or 15 mg are superior to placebo QW in HbA1c change from baseline to Week 40 	
 • Change in HbA1c from baseline
Key Secondary (controlled for type 1 error)	

 • To demonstrate superiority of tirzepatide QW 5 mg, and/or 10 mg, and/or 15 mg to placebo QW at Week 40 for: 	
 • Proportion of participants with HbA1c target values of <7.0% (<53 mmol/mol) • Change in fasting serum glucose (central laboratory) from baseline • Proportion of participants with HbA1c target values of ≤6.5% (≤48 mmol/mol) • Change in body weight from baseline • Proportion of participants with HbA1c target values of <5.7% (<39 mmol/mol)
Additional Secondary (not controlled for type 1 error)	

 • To compare tirzepatide QW 5 mg, 10 mg, and 15 mg to placebo QW at Week 40 for: 	
 • Change in daily average 7-point self-monitored blood glucose profiles from baseline • Proportion of participants who achieved weight loss of ≥5%, ≥10%, and ≥15%
Safety	

 • To compare the safety of tirzepatide QW 5 mg, 10 mg, and 15 mg to placebo QW for: 	
 • Incidence of treatment-emergent adverse events • Incidence of early discontinuation of study intervention due to AEs • Incidence of adjudicated pancreatic AEs • Change in serum calcitonin from baseline • Incidence of allergic and hypersensitivity reactions • Change in systolic blood pressure, diastolic blood pressure and pulse rate from baseline • Occurrence of hypoglycemic episodes

Objectives	Endpoints
	
• Time to initiation of rescue therapy for severe persistent hyperglycemia

CCI

Primary estimand

The primary efficacy assessment is guided by the “treatment-regimen” estimand. This estimand aims at reflecting how participants with T2DM are treated in clinical practice and takes into account both tolerability and efficacy.

The treatment-regimen estimand answers the following question of interest for the primary objective: What is the treatment difference in change from baseline in HbA1c after 40 weeks of treatment in participants with T2DM regardless of treatment discontinuation for any reason and regardless of initiation of antihyperglycemic rescue?

The treatment-regimen estimand is described by the following attributes.

- *Population:* Participants with T2DM who are inadequately controlled on diet and exercise alone, and have not been treated with any antihyperglycemic medication during the 90 days preceding the start of the study.
- *Endpoint:* Change from baseline to week 40 in HbA1c.
- *Treatment condition:* The randomized treatment regardless of adherence to treatment with or without antihyperglycemic rescue medication. Further details on study treatment and rescue therapy can be found in Study Protocol Section 6.

- *Intercurrent events*: no ICEs are defined since treatment adherence and the initiation of additional antihyperglycemic medications are a part of the treatment condition.
- *Population-level summary*: Difference in mean changes between treatment conditions.

Secondary estimand

A robustness of the primary efficacy assessment, guided by the “efficacy” estimand, will be conducted. This estimand focuses on the treatment effect if participants who underwent randomization continued to receive the study treatment without treatment discontinuation or rescue antihyperglycemic medication for severe, persistent hyperglycemia.

The efficacy estimand answers the following question of interest for the primary objective: What is the treatment difference in HbA1c change from baseline to week 40 after randomization in participants with T2DM assuming that participants had stayed on treatment and not taken antihyperglycemic rescue medication?

The efficacy estimand is described by the following attributes.

- *Population*: Participants with T2DM who are inadequately controlled on diet and exercise alone, and have not been treated with any antihyperglycemic medication during the 90 days preceding the start of the study.
- *Endpoint*: Change from baseline to Week 40 in HbA1c.
- Treatment condition: The randomized treatment. Further details on study treatment and rescue therapy can be found in Study Protocol Section 6.
- *Intercurrent event*: Intercurrent events of interest: “Treatment discontinuation for any reason” and “Initiation of antihyperglycemic rescue treatment” will be addressed using the following strategies:
 - Had participants stayed on treatment (hypothetical strategy).
 - Had participants not taken antihyperglycemic rescue medication (hypothetical strategy).
- *Population-level summary*: Difference in mean changes between treatment conditions.

The efficacy estimand will be evaluated for all primary, secondary, and tertiary efficacy objectives. The treatment-regimen estimand will be evaluated for the primary and all key secondary objectives. The population, treatment condition, and intercurrent events specified above for each estimand for the primary objective will also apply to the other efficacy objectives, and the population-level summary might be adjusted according to the endpoints of the objectives.

1.2. Study Design

Study GPIU is a multicenter, randomized, double-blind, parallel, placebo-controlled, Phase 3 study which will investigate the efficacy and safety of tirzepatide monotherapy compared with placebo in Chinese participants with T2DM, inadequately controlled with diet and exercise alone, and have not been treated with any antihyperglycemic medication during the 90 days preceding the start of the study.

Approximately, 200 participants will be randomized in a **CCI** ratio (tirzepatide 5 mg QW, 10 mg QW, 15 mg QW, and placebo QW). Participants will be stratified based on HbA1c ($\leq 8.5\%$ [≤ 69 mmol/mol] or $> 8.5\%$ [> 69 mmol/mol]), and any past prior use (Yes or No) of any antihyperglycemic medication.

Study GPIU will consist of 3 periods:

- Period I: approximately **CCI** screening/lead-in period
- Period II: **CCI** treatment period, and
- Period III: **CCI** safety follow-up period.

Study Period I (Screening and Lead-in)

Screening (Visit 1)

The purpose of screening procedures at Visit 1 is to establish initial eligibility and to obtain blood samples for laboratory assessments needed to confirm eligibility at Visit 2. The participant will sign the informed consent form (ICF) before any study procedures are performed. Procedures at this visit will be performed as shown in the Study Protocol Schedule of Assessment (Section 1.3).

Lead-in (Visit 2 to Visit 3)

At Visit 2, the screening laboratory results will be reviewed. For those participants meeting all other eligibility requirements, a dilated fundoscopic examination, performed by an ophthalmologist or optometrist, will be completed between Visit 2 and Visit 3 to confirm eligibility unless a dilated fundoscopic examination was performed by an ophthalmologist or optometrist within 90 days of study entry (Visit 1).

Additionally, at Visit 2, participants and their caregiver(s), if applicable, will receive a glucometer and training on how to perform SMBG. Participants will be asked to monitor fasting blood glucose (FBG) 4 times a week and two 7-point SMBG profiles done on 2 nonconsecutive days in the 2-week period prior to Visit 3 (randomization), Visit 9 (Week 24), Visit 11 (Week 40).

Participants will be provided diaries and will be trained as appropriate to record BG values and hypoglycemic events. During this period, participants will also be trained on disease management (symptoms of hypoglycemia and hyperglycemia) and study procedures; this training can be repeated at subsequent visits as deemed appropriate. Participants should monitor BG any time a hypoglycemic event is suspected.

Study Period II (CCI [REDACTED] treatment period)*Randomization (Visit 3)*

At Visit 3, eligible participants will perform all required baseline study procedures (including the collection of all baseline laboratory measures and electrocardiogram [ECG]) prior to randomization and prior to administering the first dose of study intervention. Participant should arrive to the clinic in the fasting state; the fasting state should have lasted at least 8 hours (water is allowed). The questionnaires (European Quality of Life-Dimensions [EQ-5D-5L] and Impact of Weight on Quality of Life-Lite Clinical Trials Version [IWQOL-Lite-CT]) should be completed before any other study procedures if the participant is not adversely affected by the fasting condition or completed after the participant has sufficiently recovered from the preceding visit procedures.

Following randomization, participants will participate in a **CCI [REDACTED]** treatment period.

Postrandomization period (end of Visit 3 to Visit 11):

The starting dose of study intervention will be 2.5 mg QW for 4 weeks, followed by an increase to 5 mg QW, for the duration of the study in the 5-mg group.

For the 10-mg group, the starting dose of study intervention will be 2.5 mg QW for 4 weeks, then the dose will be increased by 2.5 mg every 4 weeks (2.5 mg to 5 mg to 7.5 mg to 10 mg) until the 10-mg dose is reached and maintained for the duration of the study.

For the 15-mg group, the starting dose of study intervention will be 2.5 mg QW for 4 weeks, then the dose will be increased by 2.5 mg every 4 weeks (2.5 mg to 5 mg to 7.5 mg to 10 mg to 12.5 mg to 15 mg) until the 15-mg dose is reached and maintained for the duration of the study.

For the placebo group, participants will inject matched QW placebo for the duration of the study.

Visit 99

Visit 99 is only applicable to participants who discontinue the study treatment prematurely before Week 40 and decline to complete the remaining study visits but are willing to return for Visit 99 at Week 40 after randomization. This visit is critical to ensure complete data collection for the primary and key secondary endpoints.

Participants should attend this visit in the fasting state. Procedures to be completed are:

- measurement of HbA1c, FSG and weight
- listing of concomitant medications, and
- assessment of AEs.

For participants unwilling to attend this visit, their refusal to attend should be documented in the participant medical record.

Study Period III (safety follow-up period)*Safety follow-up (Visit 801) visits:*

All participants who complete the treatment period (complete Visit 11 or Visit 99) are required to complete Visit 801, a safety follow-up visit approximately 4 weeks after their last treatment visit. Participants discontinuing the study early and performing an early termination (ET) visit will also be asked to perform the safety follow-up visit, so that the safety follow-up visit will be

their final visit. During the safety follow-up period, participants will not receive study intervention. Participants may be treated with another glucose-lowering intervention decided upon by the investigator (except for prohibited antihyperglycemic medications, see Study Protocol section 6.9.1). If any new antihyperglycemic medication is initiated during the safety follow-up period, it will not be classified as rescue therapy.

Participants are also required to return any remaining study diaries to the study site at the end of this period.

The participants who complete the treatment period (complete Visit 11 or Visit 99) and safety follow-up (Visit 801) are considered as complete the study.

2. Statistical Hypotheses

The alternative hypotheses for the primary and key secondary objective are as follows,

- $H_{5,1}$, $H_{10,1}$, and $H_{15,1}$: Superiority test of tirzepatide 5 mg, 10 mg, 15 mg versus placebo in HbA1c change from baseline at Week 40 respectively.
- $H_{5,2}$, $H_{10,2}$, and $H_{15,2}$: Superiority test of tirzepatide 5 mg, 10 mg, 15 mg versus placebo in proportion of participants achieve HbA1c $<7\%$ at Week 40 respectively.
- $H_{5,3}$, $H_{10,3}$, and $H_{15,3}$: Superiority test of tirzepatide 5 mg, 10 mg, 15 mg versus placebo in FSG change from baseline at Week 40 respectively.
- $H_{5,4}$, $H_{10,4}$, and $H_{15,4}$: Superiority test of tirzepatide 5 mg, 10 mg, 15 mg versus placebo in proportion of participants achieve HbA1c $\leq 6.5\%$ at Week 40 respectively.
- $H_{5,5}$, $H_{10,5}$, and $H_{15,5}$: Superiority test of tirzepatide 5 mg, 10 mg, 15 mg versus placebo in body weight change from baseline at Week 40 respectively.
- $H_{5,6}$, $H_{10,6}$, and $H_{15,6}$: Superiority test of tirzepatide 5 mg, 10 mg, 15 mg versus placebo in proportion of participants achieve HbA1c $<5.7\%$ at Week 40 respectively.

2.1. Multiplicity Adjustment

The primary and the key secondary objectives will be evaluated align to both the treatment-regimen estimand and the efficacy estimand. No multiplicity adjustment will be made for conducting analysis aligned to the two estimands.

For analysis within each estimand, $H_{5,1}$, $H_{10,1}$, and $H_{15,1}$ will be initially tested each at 0.01667 significance level. A graphical testing scheme (Bretz et al. 2009, 2011) presented in [Figure GPIU.2.1](#) will be used to strongly control for type 1 error.

[figure not shown]

Figure GPIU.2.1. Type 1 error control strategy for primary and key secondary.

3. Analysis Sets

For the purposes of analysis, the following analysis sets are defined:

Population/Analysis Set	Population/Analysis Set
Screened population	All participants who signed informed consent
Randomized population	All participants who are randomly assigned to a treatment group.
Modified intention-to-treat (mITT) population	All randomly assigned participants who are exposed to at least 1 dose of study intervention.
Efficacy analysis set (EAS): This analysis set will be used to estimate the efficacy estimand for all efficacy objectives	Data obtained during Study Period II from the mITT population, excluding data after initiating rescue antihyperglycemic medication or stopping study intervention.
Full analysis set (FAS): This analysis set will be used to estimate the treatment-regimen estimand for the primary and key secondary objectives	Data obtained during Study Period II from the mITT population, regardless of adherence to study intervention or initiation of rescue antihyperglycemic medication.
Safety analysis set (SS): This analysis set will be used to assess the safety of study treatment	Data obtained during Study Periods II or III from the mITT population, regardless of adherence to study intervention or initiation of rescue antihyperglycemic medication.

4. Statistical Analyses

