6.6. Dose Modification

6.6.1. Tirzepatide

Please refer to Section 6.1.1 for tirzepatide administration. Study intervention dose modification is not permitted except for management of intolerable gastrointestinal symptoms.

Management of Participants with Gastrointestinal Symptoms

In participants who experience intolerable gastrointestinal symptoms (for example, nausea, vomiting, or diarrhea) at any time during the study, the following measures are recommended:

1. counseling on dietary behaviors that may help mitigate nausea and vomiting, (for example, eating smaller meals, splitting 3 daily meals into 4 or more smaller ones, and stopping eating when they feel full).
2. if symptoms persist despite #1, prescribing symptomatic medication (for example, antiemetic or antidiarrheal medication), at the investigator's discretion.
3. if symptoms persist despite #1 and #2, temporarily interrupting study intervention (omit 1 dose, the participant will take 3 of 4 doses at that dose level). Study intervention should be resumed at the assigned dose immediately, either alone or in combination with symptomatic medication, which can also be utilized to manage symptoms.

If intolerable gastrointestinal symptoms (for example, nausea, vomiting, or diarrhea) persist despite the above measures before or at Visit 5 (the scheduled visit in Week 8), the participant should discontinue the study intervention.

If intolerable gastrointestinal symptoms (for example, nausea, vomiting, or diarrhea) persist despite the above measures after Visit 5 (the scheduled visit in Week 8) the investigator should contact Lilly to consider continuing treatment at a lower maintenance dose of study intervention in a blinded fashion, for example:

- Participants at 5 mg will decrease the dose to placebo.
- Participants at 7.5 mg or 10 mg will decrease the dose to 5 mg.
- Participants at 12.5 mg or 15 mg will decrease the dose to 10mg.

If de-escalation of the tirzepatide dose is necessary, the investigator will use the IWRS to receive the appropriate tirzepatide dispensing information. If de-escalation is needed between scheduled visits, the IWRS will have unscheduled visits dedicated to providing dispensing information for

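### As worded, the efficacy analysis set keeps data collected after a 5 mg participant is moved to placebo, which does not match the efficacy estimand

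*SAP*

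**What the plan says.** **Analysis set.** SAP Section 3 and Protocol 9.2 define the efficacy analysis set (EAS) in the same words: Period II data from treated participants, "excluding data after initiating rescue antihyperglycemic medication or stopping study intervention". Only those two events remove data.

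**De-escalation.** Under Protocol 6.6.1, if intolerable gastrointestinal symptoms persist after Visit 5 (Week 8), the investigator contacts the sponsor to "consider continuing treatment at a lower maintenance dose of study intervention in a blinded fashion". Three examples follow: "Participants at 5 mg will decrease the dose to placebo"; "Participants at 7.5 mg or 10 mg will decrease the dose to 5 mg"; and "Participants at 12.5 mg or 15 mg will decrease the dose to 10mg". This can happen once, before Week 24, and the dose is not raised again. Having to discontinue study intervention is a separate, later step if symptoms continue.

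**Terms and arm.** The opening of Protocol Section 6 includes placebo in its definition of study intervention. SAP 4.1 analyses everyone in the randomised arm, whatever they actually received.

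**Estimand.** SAP 1.1 and Protocol Section 3 give the efficacy estimand two intercurrent events, treatment discontinuation and rescue, both with a hypothetical strategy. It asks for the effect "assuming that participants had stayed on treatment and not taken antihyperglycemic rescue medication". Its treatment condition reads "The randomized treatment. Further details on study treatment and rescue therapy can be found in Study Protocol Section 6". De-escalation is not mentioned there. The only SAP analysis that uses it is the gastrointestinal summary in 4.11.4.13.

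**The concern.** A participant who moves from 5 mg to placebo has started the comparator. Under the EAS wording that participant has neither begun rescue nor stopped study intervention, so every later visit up to Week 40 counts as tirzepatide 5 mg. The estimand asks what 5 mg would have done had it been continued, and a period spent on placebo does not answer that question.

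What is at stake is the meaning of the 5 mg estimate under the efficacy estimand. That estimand is secondary, but it is widely used. It has its own testing of the primary and key secondary hypotheses (SAP 2.1), and it is the only estimand for the additional secondary endpoints (SAP 4.9.2) and the efficacy subgroups (SAP 4.12.1).

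**Working it through.** The documents give no figure for the number of switches, and the planned effect, SD and discontinuation rates are redacted. The check is therefore a reading of the rules followed by illustrative arithmetic.

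**1. Follow one participant through the rules.** Randomised to 5 mg, moved to placebo between Weeks 8 and 24.
- Rescue started? No.
- Study intervention stopped? No: placebo is study intervention, and 6.6.1 treats the step as continued treatment.
- Result: later data stay in the EAS.
- Arm: tirzepatide 5 mg, by randomised assignment.
- Target of the estimand: 5 mg continued. The data and the target do not match.

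**2. Which arms.** On the scheduled titration the 10 mg and 15 mg groups have moved above 5 mg from Week 8, so the placebo step concerns the 5 mg arm. The one route by which another arm could be at 5 mg later is the restart at 5 mg after three or more missed doses (Protocol 7.1.2).

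**3. Average dilution.** Inputs: 50 participants per arm (Protocol 9.5); k switched; assumed effect of 1.5 HbA1c points; fraction of the effect lost by Week 40, f. Dilution = (k/50) × effect × f.

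| k | Share of effect, f = 1 | HbA1c points, f = 1 | HbA1c points, f = 0.5 |
|---|---|---|---|
| 1 | 2% | 0.030 | 0.015 |
| 2 | 4% | 0.060 | 0.030 |
| 3 | 6% | 0.090 | 0.045 |

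For k = 1 and f = 1, assumed effects of 1.2 to 1.8 give 0.024 to 0.036. One participant can move a responder proportion by 1/50 = 2 percentage points. Rescue after the switch would end some participants' EAS data before Week 40. It would not remove the dilution, because their worsened values before rescue remain and the repeated-measures model predicts Week 40 from them.

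**4. Power of the 5 mg HbA1c test under this estimand.** Initial alpha is 0.05/3 = 0.01667, as SAP 2.1 states. Normal approximation, 50 against 50, difference = effect × (1 − k/50), full loss:

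| Assumed effect, SD | k = 0 | k = 1 | k = 3 |
|---|---|---|---|
| 1.5, 1.2 | 0.9999 | 0.9999 | 0.9998 |
| 1.5, 1.5 | 0.995 | 0.994 | 0.989 |
| 1.0, 1.5 | 0.826 | 0.809 | 0.770 |

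The loss is negligible unless a small effect and a large SD are assumed together.

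**5. Keep or exclude.** Suppose a switcher's unseen response on 5 mg would have been d points worse than the model predicts.
- Excluding the data overstates the effect by d/50.
- Keeping the data understates it by (L − d)/50, where L is the effect lost.
- The two errors are equal at d = L/2. That is 1.5/2 = 0.75 points at full loss and 0.75/2 = 0.375 points at half loss, ignoring rescue.
- At d = 0.5, excluding is off by 0.5/50 = 0.010. Keeping is off by (1.5 − 0.5)/50 = 0.020 at full loss, or (0.75 − 0.5)/50 = 0.005 at half loss.

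Excluding is therefore closer to the target unless switchers would have responded clearly worse than predicted. Nothing in the documents settles that.

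**The case against.** **The text already gives an answer.** The definitions lead to one outcome, which is to keep the data, and the treatment condition points to Protocol Section 6, which contains the de-escalation rule. On that view the regimen includes de-escalation, and asking for something else is a preference among estimands. The first part stands. A reader might infer that the rule is open and could be chosen after unblinding with the results in view; the documents do not support that, because followed as written they fix the dataset. The second part holds for step-downs to a lower active dose, where the participant is still on tirzepatide. It does not hold for a move to the comparator, which cannot represent having stayed on 5 mg.

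**The SAP's other term.** SAP 4.1 describes the same estimand as efficacy before discontinuation of study drug. A reader might see two conflicting rules. The SAP uses that term for all arms, placebo included (for example in SAP 4.8.2, 4.11 and its event listings), so the difference is editorial.

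**Rarity.** Protocol 2.3.1 says most gastrointestinal events came during escalation, and the 5 mg arm completes escalation at Week 4. Intolerance persisting at or before Week 8 leads to discontinuation, which the EAS already excludes. A later switch requires failed counselling, medication and dose interruption, then contact with the sponsor. This stands: the event is probably uncommon.

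**Missing at random.** Exclusion relies on that assumption in people selected by intolerance. This also stands and is a reason for a sensitivity run.

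**Conclusion.** The mismatch between the EAS and the efficacy estimand is real but minor. Followed as written, data collected on placebo enter the 5 mg efficacy-estimand results and dilute them. The size is about 2% of the effect per switched participant of 50 if the whole effect is lost, or 0.03 HbA1c points at an assumed 1.5-point effect, and half that if half is lost. This is an average: an above-average responder could lose more, so 2% should not be read as a ceiling. The switch rate, effect, SD and rate of loss are assumptions, and the number of switches may be zero.

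A reader might infer that the primary result or a superiority claim is at risk. The documents do not support that. The primary treatment-regimen analysis uses the full analysis set, which keeps data regardless of adherence, so its observed values do not change. The dilution under the efficacy estimand works against tirzepatide, so no claim is inflated. This is a cheap improvement to what the 5 mg estimate means.

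**What to change.** Leave the dosing rule untouched. Before unblinding:

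1. State in SAP 1.1 and Section 3 that, for the efficacy estimand and the EAS only, a switch from tirzepatide to placebo is handled as treatment discontinuation and later data are excluded. State also that step-downs to a lower active dose remain on-treatment as part of the Protocol Section 6 regimen.
2. State that this does not by itself change the retrieved-dropout definition in SAP 4.8.2, which supplies the imputation for the primary analysis, or the disposition summaries in SAP 4.3.
3. Add one sensitivity run that keeps the post-switch data.
4. As an editorial matter only, use one term for study drug and study intervention.

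The cost is a few sentences and one extra model run. De-escalations already pass through the interactive web response system, so the flag should be available. The statistical price is three to six fewer HbA1c observations per switched participant (Visits 9 to 11 for a switch just before Week 24, Visits 6 to 11 for one just after Week 8) and reliance on missing at random for those values.
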